To investigate the effectiveness of job crafting intervention program on job crafting behavior, work meaningfulness, change attitude, adaptive and task performance among nurses at Zagazig university hospitals.

Research hypothesis:

1. After program intervention, nurses will demonstrate an increase in job crafting behavior (increasing job Resources, increasing challenging job demands, and decreasing hindering job demands).
2. Nurses participating in the intervention program will report higher levels of work meaningfulness.
3. The experimental group will demonstrate an increase in positive work attitude and decrease in negative work attitude

4. The experimental group will experience a higher adaptive performance and perform higher levels of task performance.
5. An increase in job crafting behavior is related to and predicts work meaningfulness, change attitude, adaptive and task performance among nurses

Subjects and Methods:

Research design:

The study described in ClinicalTrials.gov with the identifier NCT.....utilized a randomized control trials research design.

Administrative & Ethical Steps:

We obtained official written authorization from the Zagazig university hospitals in order to carry out our research, following the approval of ethical considerations. Formal consent and authorization for the study were also acquired from the Research Ethics Committee within the Faculty of Nursing at Zagazig University, Egypt (IRB:). Patients were duly informed about the study's objectives, and we obtained their informed written consent. They were informed of their right to decline participation, with the assurance that their decision would not impact their care. Moreover, patients were assured that they had the option to withdraw from the study at any point, even after initiation, with the assurance of maintaining their privacy and confidentiality.

Study setting :

This study was conducted at the Zagazig University Emergency Hospital, which provides a wide spectrum of health services at El Sharkia Governorate in Egypt. This hospital receives emergency cases and injuries 3 days/week from Zagazig City and other near areas, giving care for about 7.5 million people, according to the hospital most recent statistical data. The hospital is occupied with (185) beds.

Subjects:

Include staff nurses working in different departments of Zagazig University Emergency Hospital.

Sample size :

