Part (2): Job Crafting questionnaire was developed by Tims, et al. (2012). It consisted of 13 items with three subscales [1] seeking resources included 6 items e.g.(I ask others for feedback on my job Performance), [2] seeking challenges included three items, e.g.(I ask for more tasks if I finish my work), and reducing demands by using 4 items e.g.(I try to ensure that my work is emotionally less intense) . The *questionnaire* was measured on five-point ranging scale from (1) “Never” to (5) “Always”. The total score of this tool ranged from 13-65. Scores \geq [] indicated a higher perception level of job crafting behavior, scores [] indicated a moderate level, while scores [] indicated a low perception level (please reference to level). (please reference if tools used with nurse and previous reliability and consistency). The reliability of the tool was measured by Cronbach alpha coefficient and it was ranged from .87 to .92

Part (3): Work And Meaning Inventory(WAM I)

The scale was developed by Steger et al.(2012), to reflect weekly work meaningfulness by using the 10-items. The WAMI consists of three facets: positive meaning 4 items e.g. (I understand how my work contributes to my life's meaning this week), meaning making 3 items e.g. (This week, I viewed my work as contributing to my personal growth), and greater good motivations 3 items e.g.(This week, I knew my work made a positive difference in the world). All items were scored on a five-point Likert scale ranging from 1 (absolutely untrue) to 5 (absolutely true). The total score of this tool ranged from 10-50. Scores \geq [] indicated a higher perception level of work meaningfulness, scores [] indicated a moderate level, while scores [] indicated a low perception level(please reference to level). (please reference if tools used with nurse and previous reliability and consistency). . The reliability of the tool was measured by Cronbach alpha coefficient, it ranged from .60 to .81 (M = .71).

Part (4): Change attitude scale: This dependent variable was measured using 15 items from Dunham et.al (1989), to measure the affective, cognitive and behavioral dimensions of attitude towards change. It includes two subcategories; positive attitude

towards change with 7 items e.g.(I am happy at the prospect of this change), and negative attitude towards change 8 items e.g. (I find it difficult to accept new things).

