All statements were rated on a scale Likert that went from 1 (strongly disagree) to 5 (strongly agree). *Scoring system: The total score of this tool ranged from 15-75.*

The scores were categorized into highly openness to change (positive attitude) (participants who scored $> 75\%$ on attitude based questions), and (resistance) unfavorable negative attitude (participants who scored $\leq 75\%$ on attitude based questions). (please reference to level). (please reference if tools used with nurse and previous reliability and consistency). Cronbach's alphas was ($\alpha=.859$).

Part (5): Task, Contextual and Adaptive performance scales: was used for measuring task and Adaptive performance; task performance was measured by a scale developed by Williams and Anderson (1991). Seven items on task performance were measured e.g. (Fulfills responsibilities specified in job description") They were measured on a five-point ranging scale from (1) "Strongly disagree" to (5) "Strongly agree". The total score of this tool ranged from 7-35. Scores $\geq []$ indicated a high levels of task performance, scores [] indicated a moderate level, while scores [] indicated a low perception level (please reference to level). (please reference if tools used with nurse and previous reliability and consistency). . Cronbach alpha was $\alpha=.770$.

Adaptive performance: was measured on a five item scale. This originated from the preferences of the Elkerliek hospital. A sample item for adaptive performance include: "I use the screening in the quality chart to predict risk on delirium"; "I use the checklist in the care chart";"I use prevention actions and treatment interventions in my daily job". The scale ranges from (1) "Never" to 5"Extremely often". The total score of this tool ranged from 5-25. Scores $\geq []$ indicated a high levels of adaptive performance, scores [] indicated a moderate level, while scores [] indicated a low perception level adaptive performance(please reference to level). (please reference if tools used with nurse and previous reliability and consistency). . Cronbach alpha was $\alpha=.909$.

Content validity and reliability:

After the instrument was translated into Arabic, data were collected using a self-administered questionnaire. A jury of experts (5 professors & 7 assistant professors)

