Before the research started, ethical approval was given by the Scientific Research Ethics Committee at the Faculty of Nursing-Zagazig University (NO: 056). Participants were

explained the study objective and protocol, and only those who provided informed consent were included. Voluntary participation, autonomy, and confidentiality of the information gathered were confirmed.

Statistical design:

All data were collected, tabulated, and statistically analyzed using version 20.0 of the Social Science Statistical Package (SPSS), quantitative data were expressed as mean \pm SD and range, and qualitative data were expressed as absolute frequencies (number) & relative frequencies (percentage). Paired t-test was used to compare normally distributed variables between two dependent groups. P.

Pearson correlation coefficient has been determined to determine the relationship between different variables of the sample,(+) sign indicates direct correlation and-) (sign indicates reverse correlation, even values close to 1 indicate strong correlation and values close to 0 indicate weak correlation. All testing was two-sided. P-value < 0.05 was deemed statistically significant (S), and p-value < 0.001 was considered highly statistically significant (HS), and p-value ≥ 0.05 was considered statistically insignificant (NS).

References

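### The two-class scoring of change attitude labels a nurse who is neutral on all 15 items as resistant, whichever way the 75% cut is read

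*Protocol*

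**What the plan says.** Part (4) of the Protocol's Tools of data collection measures attitude to change with 15 items in two subcategories. The positive one is described as "towards change with 7 items e.g.(I am happy at the prospect of this change"; the negative one has 8 items. On the response scale it says: "All statements were rated on a scale Likert that went from 1 (strongly disagree) to 5 (strongly agree". The total is given as 15-75.

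The scoring rule opens with "The scores were categorized into highly openness to change (positive attitude", which applies above 75%. The only other class, for 75% or less, is labelled "resistance) unfavorable negative attitude". The text does not say what the 75% is a percentage of, or whether the negative items are reverse-scored before the total is formed. A drafting note asks for a reference for the levels.

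The other four scales (job crafting, work meaning, task performance, adaptive performance) each have three levels with the cut-offs still blank, in the pattern "scores [] indicated a moderate level, while scores [] indicated a low perception level".

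Under Statistical design, "qualitative data were expressed as absolute frequencies (number) & relative frequencies (percentage". That section names no test of the attitude classes. Item 3 of the Research hypothesis reads: "The experimental group will demonstrate an increase in positive work attitude and decrease in negative work attitude".

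**The concern.** A label that says a nurse resists change should apply only to nurses whose answers lean that way. Here the lower class takes in everyone who does not reach a high threshold, including a nurse with no leaning in either direction. A high cut for being highly open is a reasonable choice. Calling everyone below it resistant is not, because failing to be highly open and being unfavourable are different states.

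What is at stake is descriptive reporting. If the classes are tabulated as numbers and percentages, the share with a negative attitude will include neutral nurses, and possibly mildly favourable ones, in both arms at baseline, post-intervention and three months. A nurse could also move a long way in the favourable direction and still be counted as resistant.

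**Working it through.** **Inputs (Protocol, Part 4).** 15 items, 7 positive and 8 negative; responses 1 to 5, so the midpoint is 3; cut at 75%, with a score of exactly 75% in the lower class.

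**Step 1: the plan's own range.** 15 × 1 = 15 and 15 × 5 = 75. The stated 15-75 is reproduced.

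**Step 2: where the cut falls.**
- 75% of the maximum: 0.75 × 75 = 56.25. Totals 15-56 are in the lower class and 57-75 in the upper.
- 75% of the range: 15 + 0.75 × (75 − 15) = 60. Totals 15-60 are in the lower class and 61-75 in the upper.

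**Step 3: the all-neutral nurse.** The total is 15 × 3 = 45. Reversal turns a 3 into a 3, so this holds with or without it.
- Against the maximum: 45/75 = 60%.
- Against the range: (45 − 15)/60 = 50%.
- If the 75% means the share of items answered favourably: 0/15 = 0%.

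All three are at or below 75%, so this nurse is labelled negative on every reading.

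**Step 4: if the negative items are reversed and the cut applies to the total.** Totals above 45 then lie on the favourable side of neutral.
- 75% of maximum: 46-56 are favourable but labelled negative (56/15 = 3.73 per item).
- 75% of range: 46-60 are favourable but labelled negative (60/15 = 4.0 per item, the favourable answer 4 to every item).
- Example: the favourable answer 4 on the 7 positive items and 3 on the 8 negative items gives 7 × 4 + 8 × 3 = 52, which is 69% of the maximum and 62% of the range. It is labelled negative on both.
- Of the 61 possible totals, 30 (15-44) lie below neutral, but 42 (15-56) or 46 (15-60) carry the negative label.
- A nurse moving from 30 to 56 is in the negative class both times.

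**Step 5: if the negative items are not reversed.**
- Most favourable nurse: 7 × 5 + 8 × 1 = 43 (57% of maximum).
- Most resistant nurse: 7 × 1 + 8 × 5 = 47 (63% of maximum).

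Both are labelled negative, and the most resistant nurse has the higher total. A nurse who strongly agrees with every item of both kinds scores 75 and is labelled positive. On this reading the total does not order attitude.

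**Step 6: if the 75% is a share of items.** Favourable answers on 11 of 15 items give 73% and the negative label; 12 of 15 give 80% and the positive label. The boundary is then not at 56 or 60: a nurse at 4 on 12 items and 1 on 3 items (items scored in the favourable direction) totals 12 × 4 + 3 × 1 = 51 and is positive.

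**The case against.** Four arguments can be made for the plan.

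**The favourable range is conditional.** A reader might infer that favourable nurses scoring up to 56 are certainly counted as negative. The protocol does not support that as a flat statement. It needs reversal of the 8 negative items and a cut on the total, and neither is written down. Steps 5 and 6 show that the 46-56 or 46-60 range does not carry over to the other readings. This stands, and it limits the unconditional claim to the all-neutral nurse.

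**Hypothesis 3 has another route.** A reader might infer that the two halves of hypothesis 3 cannot be told apart. With two exhaustive classes the positive and negative percentages are indeed complements, but Part (4) also defines separate positive and negative subscales. Their scores can show a rise in one and a fall in the other, and the hypothesis does not mention class percentages. This also stands.

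**No named analysis uses the classes.** Statistical design lists means with SD and range, a paired t-test and Pearson correlation. Its sentence on qualitative data is general and does not mention change attitude. The same cut would apply to both arms at every assessment, so no bias between arms has been shown. This keeps the point minor.

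**The rule is provisional.** A supporting reference is still to be added. That could justify a threshold for high openness, but not a label that calls an all-neutral response unfavourable. Unlike the blank cut-offs of the other scales, this cut and both labels are already filled in. This argument does not rescue the rule.

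**Conclusion.** The labelling is wrong as written, and the point is minor. That an all-neutral nurse (45) is classed as negative needs no assumption beyond 3 being the neutral answer on a 1-5 agreement scale.

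The wider statement, that totals of 46-56 or 46-60 are favourable but labelled negative, rests on reverse-scoring and a total-score base. If the negative items are not reversed, the fault is worse: the total and its classes do not measure attitude in a consistent direction.

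Means, paired t-tests and correlations on the subscale scores are not affected by the classes. Any reported number or percentage with a negative attitude is. On a correctly reversed total it would be overstated in each arm at each assessment by the nurses who score from 45 up to the cut. A reader might want a head count, but the protocol gives no mean or SD for this scale, so it supports none.

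**What to change.** In the scoring paragraph of Part (4):

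- State that the 8 negative items are reverse-scored when the 15-75 total is formed. The negative subscale itself can stay unreversed, so that a fall means a less negative attitude.
- State whether the 75% is of the maximum (highly open from 57) or of the range (highly open from 61).
- Keep scores above 75% as highly open, and then do one of two things. Either rename the lower class as not highly open, or use three classes: resistant or negative for 15-44, a middle class for 45-56 or 45-60, and highly open above that. The second option matches the three-level layout of the other four scales.
- State that hypothesis 3 is assessed on the separate positive and negative subscale scores and not on the two-class percentage.

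The cost is a few sentences of scoring text and a relabelled variable in the analysis file. No new data are needed.

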burnout, and create a positive and fulfilling workplace. Nurses experiencing meaning in their tasks are more likely to exhibit a sense of purpose, positively impacting their job performance, job retention, and the quality of patient care they deliver (10,11).

The importance of job crafting in the nursing context is underscored by its impact on the meaningfulness of tasks and adaptive performance. When nurses engage in job crafting, they are more likely to find their work personally meaningful, as they align their roles with their values and preferences. Moreover, job crafting enables nurses to enhance their adaptive performance by tailoring their roles to better navigate the dynamic and challenging healthcare environment. In doing so, nurses can optimize their effectiveness, job satisfaction, and overall well-being in their demanding profession (12,13).

Enhancing job crafting among nurses is imperative for improving their job satisfaction, well-being, and patient care outcomes. Despite existing research on job crafting, there is a notable lack of studies specifically addressing how to enhance this practice among nurses. Job crafting allows nurses to tailor their roles, providing a sense of autonomy, stress reduction, and increased engagement. By empowering nurses to adapt to evolving healthcare environments and fostering positive team dynamics, job crafting contributes to better patient care and the retention of skilled professionals(14-16). Research addressing this gap is essential to provide practical guidelines for healthcare organizations seeking to implement effective initiatives that enhance job crafting and, subsequently, the overall well-being and effectiveness of nursing professionals.

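### The sample items for adaptive performance record use of care charts and care actions, not adaptation to change, so the adaptive-performance parts of the aim and of hypotheses 4 and 5 are not validly tested as described

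*Protocol*

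**What the plan says.** Adaptive performance appears in the title, in the Aim of the study and in two hypotheses. Hypothesis 4 states: "The experimental group will experience a higher adaptive performance and perform higher levels of task performance". Hypothesis 5 has job crafting behaviour predicting four outcomes, adaptive performance among them.

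The Introduction links the construct to flexibility and responsiveness as nursing situations evolve, and says that "job crafting enables nurses to enhance their adaptive performance by tailoring their roles to better navigate the dynamic and challenging healthcare environment".

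The instrument is in Tools of data collection, Part (5). Adaptive performance "was measured on a five item scale", and of its source the protocol says: "This originated from the preferences of the Elkerliek hospital". Three sample items are given:

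- "I use the screening in the quality chart to predict risk on delirium"
- "I use the checklist in the care chart"
- "I use prevention actions and treatment interventions in my daily job"

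Responses run from 1 (Never) to 5 (Extremely often), and "The total score of this tool ranged from 5-25". A Cronbach alpha of .909 is given without the sample it came from. The prompt to cite earlier use in nurses and earlier reliability is still unfilled. According to Study setting, the trial takes place at Zagazig University Emergency Hospital.

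**The concern.** The protocol describes one construct and measures something else under the same name. How often a nurse uses a screening chart, a checklist or a set of care actions is a matter of care routine. How well a nurse adjusts when the work changes is a different property, and a nurse can be high on one and low on the other.

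A between-arm difference on this score would be reported as a gain in adaptability when the items shown point to use of care tools. A finding of no difference would not count against an effect on adaptability. The protocol itself fixes the instrument, and no later analysis can make the items measure another construct.

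**Working it through.** The question is what the items measure, so the check is mainly a comparison of texts. The arithmetic covers only the score range and the share of the score that can be seen.

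**1. Score range.** Five items scored 1 to 5 give 5 × 1 = 5 to 5 × 5 = 25. This matches the stated range.

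**2. Visible share of the score.** The three items shown contribute 3 to 15 points, a span of 12. The two not shown contribute 2 to 10, a span of 8. The total span is 25 − 5 = 20, so the visible items carry 12/20 = 60% of it and the unseen items 40%.

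**3. Items against the construct.**

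| Item shown | What it records | Names delirium | Names a chart | Asks about adapting to change |
|---|---|---|---|---|
| Delirium risk screening | frequency of using a screening tool | yes | yes | no |
| Care-chart checklist | frequency of using a checklist | no | yes | no |
| Prevention and treatment actions | frequency of carrying out care actions | no | no | no |

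One of three names delirium, two of three name a chart, and none of three asks about flexibility, responsiveness or changing one's role. A nurse who follows the same routine on every shift, altering nothing, could score 3 × 5 = 15 out of 15 on these items.

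**4. Does anything else in the protocol supply the missing link?**

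- *Origin.* The scale is traced to the preferences of one hospital, which is not the trial site. The only listed reference naming that hospital is an interview, not a validation study.
- *Local applicability.* Nothing says that a quality chart with delirium screening, or the care-chart checklist, is in use at the study hospital.
- *Alpha of .909.* Internal consistency shows that items move together. Items on chart use can agree closely with one another without measuring adaptability.
- *Expert jury.* Content validity and reliability reports that twelve academics (5 + 7) reviewed the translated questionnaire and that adjustments followed. This is one statement for the whole questionnaire, and no change to these items is described.

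**5. Reach.** The five named outcomes are job crafting behaviour, work meaningfulness, change attitude, adaptive performance and task performance. One of the five is affected. In hypothesis 4 it is one of two, because task performance has a separate seven-item scale. In hypothesis 5 it is one of four predicted outcomes.

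**The case against.** The strongest reply is that the evidence is partial. Two of the five items are not shown, and neither is the final Arabic wording. A jury reviewed content and face validity and a pilot followed, so the fielded items may differ from the samples. The third sample item is generic and could apply on any ward, so the scale cannot be called five items on another hospital's delirium charts. The open prompt for references also shows that the authors knew the tool's support was still to be documented.

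Much of this stands and limits the claim to the items shown and to the scale as described. It does not remove the mismatch: the protocol chose these three items to illustrate the outcome, they carry 60% of the score span, and none touches the construct in the Introduction. An unfilled prompt is not evidence of validity.

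A reader might infer more, and the document does not support these readings:

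- *Hypothesis 4 as a whole fails.* It does not, because task performance is measured separately.
- *Answers would pile up at Never in both arms, leaving no power, or any effect would shrink in proportion to the nurses without such charts.* Both depend on local chart use, which the protocol does not give. The third item does not depend on a chart, and two items are unknown.
- *The program should have taught delirium charting.* An outcome need not be part of the training content. Adaptive performance is meant to follow from job crafting, so its absence from the sessions is not a fault.

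**Conclusion.** The concern holds for the scale as described. The items shown measure self-reported use of screening, a checklist and care actions; the protocol's own account of adaptive performance is about adjusting to change. The adaptive-performance part of the aim, of hypothesis 4 and of hypothesis 5 is therefore not validly tested. The other four named outcomes are unaffected by this point.

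No numerical bias or loss of power is claimed, because the protocol gives no figure from which either could be derived. The conclusion assumes that the three sample items represent the fielded scale. It would need another look if the full five-item wording, with evidence of its validity and local applicability, showed otherwise.

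**What to change.** Print all five items as fielded in Part (5), and state whether the charts they mention are used at the study hospital. The next step depends on timing, which should be confirmed: Field work and Pilot study are written in the past tense, with fieldwork placed in March to August 2023, while the document is dated 8-1-2024.

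- **If baseline data are not yet collected:** replace the items with ones asking how nurses adapt to changes in tasks, tools and roles, and pass them through the same expert jury and pilot. The cost is a small amount of jury and pilot work.
- **If data are already collected:** replacement is no longer possible. Rename the outcome to what the items measure, such as self-reported use of screening, checklist and care actions, in the aim, hypotheses 4 and 5 and the analysis, and draw no adaptive-performance conclusion from it. Check the name against the two items not shown. The cost is wording only, at the price of a narrower claim.
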